The current pathway to obtain prostate tissue for histological diagnosis of CaP is by transrectal ultrasound-guided systematic biopsy (TRUSB) of the prostate, usually following the detection of a raised serum PSA level and/or suspicious rectal examination findings. TRUSB has been the standard prostate tissue sampling technique for men suspected with PCa for over 30 years. It is an office-based procedure carried out under local anaesthesia (LA), with 10 to 12 biopsy cores directed towards the lateral peripheral zones of the prostate thought to harbour majority of cancers [7]. However, there are still various well-known cancer detection limitations and patient safety problems associated with TRUSB.

Firstly, a very significant portion of tumours are being missed with the TRUSB technique [8]. It has been well- known that over 30% of patients with low risk PCa on TRUSB have been found to harbour clinically significant PCa [9]. Many of these tumours missed on TRUSB are located in the anterior and apical regions of the prostate, which TRUSB is difficult to access, in particular in patients with a large prostate volume

Secondly, TRUSB requires the biopsy needle to penetrate through the bowel (rectum). This results in high risk of developing sepsis following biopsy, despite all patients undergoing the procedure being started on antibiotics prophylactically. This is a serious complication which can potentially be life-threatening. Our previous study has already demonstrated a high prevalence of fluoroquinolone-resistant and ESBL-producing rectal flora in our local population in Hong Kong [10]. The risk of developing post-biopsy sepsis in Hong Kong is high.

Transperineal prostate biopsy (TPB) has been developed to provide a more comprehensive biopsy method to improve cancer detection rate by directing biopsy cores through the perineal skin. Theoretically, TPB enables access to sample the entire prostate, in particular the anterior and apical regions which are not easily accessible through the standard TRUSB method. By sampling the prostate using

biopsy needles directly inserted through the perineal skin rather than bowel, the risk of sepsis is reduced. However, this technique requires multiple needles traversing through the perineum, and requires to be carried out under general anaesthesia (GA). Another disadvantage is a stabilising stepping unit is required to provide a consistent alignment of the ultrasound probe against the prostate in order to carry out the biopsies. Such stabilising stepping units are costly.

A novel but simple transperineal access system device known as PrecisionPoint (Perineologic, Cumberland, MD, USA) has been developed to tackle the aforementioned limitations of TPB. This revolutionary device utilises a single access needle cannula mounted directly on to the ultrasound probe, which acts as an access point traversing through the perineal skin. This design minimises the number of needle punctures through the skin, enabling TPB to be carried out under LA. A stabilising stepping unit is not required with this technique. The device has gained the United States Food and Drug Administration (FDA) approval [11], and results from small contemporary series have already been published with very promising results in terms of cancer detection rate and safety [12].

TRUSB has a poor cancer detection rate and is associated with potentially fatal septic risk. TPB, if able to be carried out under LA as an office-based procedure, can potentially provide a better cancer detection rate with significantly reduced sepsis risk. It has fundamentally a very high potential to become the new gold standard in obtaining prostate tissue for histological diagnosis of PCa.

With an increasing number of men in Hong Kong with elevated serum PSA suspicion of PCa needing prostate biopsy, we strongly feel that it is fundamental to carry out a study to determine the most effective, safe and tolerable prostate biopsy technique which fits with the clinical practice in Hong Kong.

Aim of study

To evaluate whether TPB using a noval transperineal access system under LA is superior to standard 12-cores TRUSB in detecting prostate cancer (PCa), in patients with clinical suspicion of PCa with no prior prostate biopsy.

Other objectives of the study include:

- > To assess whether LA TPB has reduced post-biopsy sepsis rate
- To assess whether patient tolerability with LA TPB is non-inferior to standard TRUSB

Study design and method

All patients referred with a raised serum PSA or abnormal DRE will be seen in the urology specialist unit outpatient clinic (OPD), where patients will be screened and assessed for eligibility for the study. All patients must satisfy all inclusion criteria and none of the exclusion criteria outlined in the table below.

Inclusion criteria	Exclusion criteria
1. Patients between ages 40 –	1. Patients who are unable to
80	provide written informed
	consent
2. Serum PSA ≤20ng/mL	Known history of prostate
	cancer
Suspected tumour clinical	Contraindication to prostate
stage ≤T2 on DRE	biopsy
No previous history	Had pre-biopsy mpMRI
prostate biopsy	
5. Medically fit to undergo	5. Rectal abnormality precluding
procedures according to	transrectal ultrasound
study protocol	

If eligible, informed consent will be obtained. Baseline characteristics will be recorded, such as age, height, weight, allergies, past medical history, family history of PCa, drug history, presenting PSA and DRE findings. Baseline urine and blood samples will be taken. Baseline IPSS, EQ-5D-5L and IIEF questionnaires will be filled by each participant. Eligible patients will be randomized to either the LA TRUSB arm or the LA TPB arm. Randomisation will be executed per participant with a third-party statistical software using a computer-generated randomization tool, following completion of informed consent procedure. Equal allocation between both arms will be performed, using random permuted blocks of varying size. In order to ensure allocation concealment, block sizes will not be disclosed and randomisation codes will be obtained through a web-based application.

Procedures will be carried out within 30-60 days following first visit. Procedure in each arm will be carried out according to protocols described below within 60 days of randomisation. All patients on anticoagulants will be advised to stop 7 days prior to biopsy.

For the superiority hypothesis, based on assumptions from results from previous preliminary studies, a sample size of 330 subjects (165 per group) will achieve 80% power to detect superiority of LA TPB over TRUSB. The calculation used a one-sided Z test assuming superiority margin of 10% and the significance level at 0.05. Estimating up to 10% of patients will withdraw from the study or loss to follow-up, 364 patients will need to be recruited for the study (182 patients per arm).

Patient recruitment and enrollment will take place at urology outpatient clinics at a tertiary university teaching hospital. In 2017, on average 16 biopsy-naïve men with raised serum PSA underwent TRUSB per month. It is therefore estimated that the study will complete within 26 months of commencement. The start date of the study will be 1st April 2019, and the estimated completion date for recruitment will be 1st June 2021.

Statistical analysis

Primary outcome analysis will be based on intention to treat sample as well as per protocol sample.

Primary endpoint is difference in proportion of patients with PCa detected between the two cohorts based on histopathological analysis. Absolute differences in PCa detection rate will be calculated with 95% CIs. If lower bound of 97.5% CI for the difference in cancer detection rates of LA TP biopsy compared with TRUS biopsy is greater than -5%, then TP biopsy will be deemed non-inferior. If lower bound is greater than 0, TP will be deemed superior. Comparisons will be made concerning the basic characteristics between the two arms of participants. If any imbalance were identified, a multivariable logistic regression analysis will be carried out, with clinically significant PCa as the dependent variable and group as the independent variable. Any baseline characteristics imbalance will be used as a covariate.

Effect sizes concerning secondary outcomes will be presented with 95% CIs. For binary outcomes, differences between the two arms will be calculated with 95% CIs. Any imbalance between the two arms will again be accounted for with a multivariable logistic regression analysis. For continuous outcomes, mean differences in outcomes between the two study arms will be calculated with 95% CIs. Imbalances identified between the two groups will be accounted for in a multivariable linear regression analysis. Non-parametric test will be used if any secondary outcomes were found not normally distributed. All statistical analysis will be carried out using the SPSS software.

Primary end-point

Primary outcome is proportion of participants identified with PCa, assessed on a per patient basis from each individual's biopsy histopathological analysis report (i.e. comparison of absolute cancer detection rate). Definition of PCa is presence of any PCa regardless of grade on histopathology. Definition of clinically significant PCa is any core containing Gleason grade 3+4 disease or above. Timeframe for

assessment will be when histopathology reports are available, usually expected to be within 14 days following biopsy procedures.

Secondary end-points

Secondary outcomes, tools for assessment, and their corresponding timeframe for assessment are summarized in table below.

Secondary outcomes	Assessment tool	Timeframe for
	(if applicable)	assessment
Procedure tolerability	Visual Analogue	Immediately following
	Scale (VAS)	test
Health-related quality of	EQ-5D-5L	Baseline, 24 hours post-
life and patient	questionnaire,	biopsy, and 30 days
satisfaction	IPSS, IIEF	post-biopsy
Proportion of men	Either:	1 week to 30 days post-
developing sepsis	1) admission to	biopsy
	hospital for	
	urosepsis; or	
	2) Presence of	
	rittines in unne at	
Detection rates of	Histopathology	When histonathology
natients with clinically	report	results available
significant PCa (Gleason		expected to be within 14
3+4 or higher)		days following biopsy
Maximum cancer core	Histopathology	When histopathology
length (MCCL, mm)	report	results available,
3 (, , ,		expected to be within 14
		days following biopsy
Proportion of men go on	Clinical records,	After treatment
to undergo definitive	patient interview	decision, expected to be
curative treatment for		within 30 days following
local disease (including		biopsy
surgery and		
radiotherapy)		
Procedure times	Time from start of	During test
(minutes)	ultrasound probe	
	insertion to probe	
Cost por diagnosis of		20 dava post biopay
cost per ulagriosis Of		ou days post-biopsy

Data Access and Handling

To protect patient privacy, all research data will be handled in line with Hospital Authority's or Hospital's policy in handling/storage/destruction of patients' medical records. They would be locked in cabinets where the department/ward keep patients' medical records. Electronic data would be saved in secured computer of the hospital with restricted access. USB Device would not be used for patient information for personal data.

Personal data (name, HKID, address and any other personal identifiable information) will not be recorded on the projects' data sheets or electronic files. A study code will be used.

Any documents or electronic files containing personal identifiable information would be considered as part of the medical record and will be dealt with the same stringent regulations of security according to the hospital policies. The principal investigator/co-investigator will be responsible for the execution of data protection.

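### The sample size uses one-sided 0.05 and a 10% superiority margin, but superiority is decided by a 97.5% bound above 0, so the stated 80% is not the power of the stated rule

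*Protocol*

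**What the plan says.** The Aim of study sets a superiority question for cancer detection: transperineal biopsy (TPB) against 12-core transrectal biopsy (TRUSB).

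- **Sizing** (Study design and method, sample size paragraph): "a sample size of 330 subjects (165 per group) will achieve 80% power to detect superiority of LA TPB over TRUSB". The test is then described: "The calculation used a one-sided Z test assuming superiority margin of 10% and the significance level at 0.05". The detection rates are not given; the calculation is only said to be "based on assumptions from results from previous preliminary studies".
- **Decision** (Statistical analysis): differences are reported as follows: "Absolute differences in PCa detection rate will be calculated with 95% CIs". The verdict rests on a different level: "If lower bound of 97.5% CI for the difference in cancer detection rates" is above -5%, TPB is non-inferior. Then: "If lower bound is greater than 0, TP will be deemed superior".
- **Non-inferiority elsewhere**: the Aim of study uses the term only for another outcome: "To assess whether patient tolerability with LA TPB is non-inferior to standard TRUSB".

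**The concern.** Two rules are stated for one primary comparison, and they differ in two respects.

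1. **Error level.** Sizing is at one-sided 0.05. A 97.5% lower bound is one-sided 0.025, or one-sided 0.0125 if it is the lower limit of a two-sided 97.5% interval. The text does not say which.
2. **Null value.** A superiority margin of 10%, read literally, tests whether the difference exceeds 10 points. The decision rule asks only whether it exceeds 0.

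The stricter error level lowers power and the lower threshold raises it. A reader therefore cannot tell whether the trial is short of power or much larger than its rule requires. If the margin was meant, some results would be called superior by the decision rule although the test used for sizing would fail.

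**Working it through.** **Inputs from the protocol:** 165 evaluable per arm, equal allocation, one-sided 0.05, 10% margin and 80% power (Study design and method); 97.5% bound with threshold 0 (Statistical analysis). **Not in the protocol:** the detection rates. The 80% therefore cannot be reproduced directly. The rates below are assumptions, chosen as those that would make the protocol's 80% true.

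**Formula** (unpooled Z test, rates p1 on TRUSB and p2 on TPB, d = p2 - p1, null value m):

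SE = sqrt([p1(1-p1) + p2(1-p2)]/165); power = Phi((d - m)/SE - z)

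Here z = 1.645 at one-sided 0.05, 1.960 at 0.025 and 2.241 at 0.0125.

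**Reading A: 10 points is the difference to detect, m = 0.** Solving for 80% at one-sided 0.05 gives 11.2% vs 21.2% (or its mirror image, 78.8% vs 88.8%).

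- SE = sqrt((0.0995 + 0.1671)/165) = 0.0402, and d/SE = 2.487.
- As sized: Phi(2.487 - 1.645) = 80%.
- One-sided 97.5% bound: Phi(2.487 - 1.960) = 70.1%.
- Two-sided 97.5% interval: Phi(2.487 - 2.241) = 59.7%.

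The fall from 80% to 70.1% or 59.7% does not depend on the rates. With the null unchanged, power is Phi(1.645 + 0.842 - z).

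**Reading B: a true margin, m = 0.10.** Solve for the d that gives 80% at one-sided 0.05, then apply the rule with threshold 0:

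| TRUSB rate (assumed) | d needed | Power, bound > 0, one-sided 0.025 | Power, bound > 0, one-sided 0.0125 |
|---|---|---|---|
| 10% | 20.7 points | 99.8% | 99.5% |
| 20% | 22.3 points | 99.5% | 98.8% |
| 30% | 23.1 points | 99.2% | 98.4% |
| 40% | 23.3 points | 99.2% | 98.3% |
| 45% | 23.2 points | 99.2% | 98.3% |

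Keeping the 10% threshold and changing only the bound again gives 70.1% or 59.7%.

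**Can the two mismatches cancel under reading B?** That requires d/SE - z = (d - 0.10)/SE - 1.645, so SE = 0.10/(z - 1.645). This is 0.32 for the one-sided bound and 0.17 for the two-sided interval. The largest possible SE at 165 per arm is sqrt(0.5/165) = 0.055, so they cannot cancel at any rates.

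**Effect on the verdict under reading B**, assuming 50/165 (30%) on TRUSB and Wald limits:

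- 67/165 on TPB: difference 0.1030, lower one-sided 97.5% bound 0.0004. The decision rule declares superiority.
- 80/165: lower one-sided 95% bound 0.095, below 0.10. The test as sized fails.
- 81/165: difference 0.1879, lower one-sided 95% bound 0.1009. The test as sized succeeds.

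Results from roughly 67 to 80 of 165 get opposite verdicts.

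**Size that restores 80%** at one-sided 0.025, null unchanged: 165 x (1.960 + 0.842)^2/(1.645 + 0.842)^2 = 209.5, so 210 evaluable per arm. At one-sided 0.0125 it is 254.

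**The case against.** The best defence is that the Statistical analysis section gives a usable rule. A bound above 0 is ordinary superiority, matches an aim that names no margin, and at 0.025 or 0.0125 is stricter than the sizing level. The risk of a false claim against a null of 0 is therefore not inflated. Under reading B the trial is simply generous in size. All of this stands, and it is why no direction is claimed here. It defends the rule but not the 80%, which belongs to a different test.

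A second defence is that the 97.5% bound is probably one-sided, since it then equals the lower limit of the two-sided 95% interval reported beside it. That is the more natural reading, and the 95% and 97.5% statements then agree. The mismatch of 0.025 against 0.05 remains. The 60% figures apply only if the interval is two-sided.

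Third, the example counts depend on the interval method, which the section does not name. With Newcombe or Agresti-Caffo limits the cut-offs become 68 and 82 instead of 67 and 81. The wide zone of disagreement remains.

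Finally, testing -5% and then 0 on the same bound is a standard nested sequence that needs no extra error allowance. The non-inferiority step is therefore a lesser point: neither the aim nor the sizing addresses it for detection.

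**Conclusion.** The concern holds. It is an internal inconsistency in the primary success criterion and its power, visible in the protocol's own text; no calculation in the protocol is shown to be wrong. Under the decision rule as written, the power of 165 per arm is about 70% if the sizing was against 0 (60% if the interval is two-sided). It is about 99% (98.3% to 99.8% across TRUSB rates of 10% to 45%) if a true 10% margin was used. Neither reading gives 80%.

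The fall to 70% follows from the error level alone and needs no assumed rates. The figures near 99% rest on the assumed TRUSB rates and the unpooled Z test. Whether the trial is underpowered or oversized cannot be decided from the protocol. This should be corrected because the main claim of the trial depends on it.

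**What to change.** Use one null value and one one-sided error level in both the sample size paragraph and the Statistical analysis section.

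- **Rule.** For example: TPB is superior if the lower limit of the two-sided 95% confidence interval for the difference (the same as a one-sided 97.5% bound) exceeds 0. Change the sizing level to one-sided 0.025 to match. Using one-sided 0.05 in both places would also remove the mismatch in level.
- **Sidedness.** State that the 97.5% bound is one-sided, so that it agrees with the reported 95% interval.
- **Meaning of 10%.** Replace the margin with the two assumed detection rates. If a margin is truly intended, set the success threshold at 10% instead of 0; that changes the success criterion and is more than an edit of wording.
- **Power.** Restate it for 165 per arm. At one-sided 0.025 it is about 70% for a planned 10-point difference or a retained 10% margin, and about 99% if 21 to 23 points was planned and the threshold stays at 0.
- **Non-inferiority.** Label the -5% step as one that the aim and the sample size do not address.

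**Cost:** wording in two sections and one recalculation, with no extra patients if the restated power is accepted. Keeping 80% at one-sided 0.025, for a 10-point planned difference or a retained margin, takes 210 evaluable per arm instead of 165. Inflated as the protocol does it (165 x 1.10 = 181.5, so 182), that is 210 x 1.10 = 231 recruited per arm, or 462 in total against 364.

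### The recruitment target of 364 covers a loss of about 9.3%, not the stated 10%: a minor slip in the inflation step

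*Protocol*

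**What the plan says.** The sample-size paragraph of the Protocol, under Study design and method, fixes three numbers.

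- The required size: "a sample size of 330 subjects (165 per group) will achieve 80% power to detect superiority of LA TPB over TRUSB".
- The allowance: "Estimating up to 10% of patients will withdraw from the study or loss to follow-up".
- The resulting target: "364 patients will need to be recruited for the study (182 patients per arm").

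The test behind the 330 is described as follows: "The calculation used a one-sided Z test assuming superiority margin of 10% and the significance level at 0.05". Allocation is 1:1 ("Equal allocation between both arms will be performed, using random permuted blocks of varying size"). The paragraph does not give the inflation formula. Nor does it give the detection rates behind the 330, saying only that it is "based on assumptions from results from previous preliminary studies".

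**The concern.** An allowance for loss should return the required number once the loss has occurred. The 10% is expressed as a share of patients who withdraw or are lost, so its base is the number recruited. The target should then satisfy target × 0.9 ≥ 330, and 364 does not.

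What is at stake is whether the sample-size statement agrees with itself. Anyone who takes the target and applies the stated allowance gets fewer men than the same paragraph says are needed. The effect on power is very small.

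**Working it through.** **Inputs**, all from the sample-size paragraph: 330 men (165 per group), 80% power, one-sided 0.05, loss up to 10%, target 364 (182 per arm), 1:1 allocation.

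**1. Reproducing the stated target.** Multiplying by (1 + 0.10): 165 × 1.1 = 181.5, rounded up to 182 per arm; 2 × 182 = 364. This matches exactly.

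**2. Applying the allowance to the target.** 364 × 0.9 = 327.6, or 163.8 per arm, which is 330 − 327.6 = 2.4 men short. In whole men per arm:

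| Losses out of 182 | Loss rate | Men left in the arm |
|---|---|---|
| 17 | 9.34% | 165 |
| 18 | 9.89% | 164 |

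Eighteen losses in an arm are still within the stated allowance, yet leave one man fewer than required.

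**3. The loss that 364 does cover.** 1 − 330/364 = 0.0934, or 9.3%.

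**4. The target that matches 10%.** Dividing by (1 − 0.10): 330/0.9 = 366.7, rounded up to 367. Per arm, 165/0.9 = 183.3, rounded up to 184, or 368 in total. That is 3 to 4 men above 364, about 1%. If only whole losses are counted, 183 per arm (366) would just suffice: 10% of 183 is 18.3, so at most 18 men are lost and 165 remain.

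**5. The effect on power.** Assume that 330 men give exactly 80%. For a Z test whose standardised effect grows with the square root of the sample size,

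power(n) = Φ[(z₀.₉₅ + z₀.₈₀) × √(n/330) − z₀.₉₅], with z₀.₉₅ + z₀.₈₀ = 1.645 + 0.842 ≈ 2.486.

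- n = 327.6: Φ(2.486 × 0.9964 − 1.645) = 79.75%.
- n = 327: 79.68%.
- n = 327.6 with a two-sided 0.05 test instead: 79.71%.

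This formula needs no detection rates. As a check, power for two proportions was computed directly at 163.8 and at 165 per arm, with assumed TRUSB detection rates from 10% to 50% and, for each, the TPB rate that calls for about 165 per arm. These rates are assumptions, as the Protocol gives none. The drop was 0.25 to 0.26 percentage points one-sided and 0.29 two-sided across the whole range.

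**The case against.** The strongest reply is that nothing of consequence is wrong. It has four parts.

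- **Precision.** The Protocol states power as a whole percentage, and 79.7% rounds to 80%. This stands. A reader might infer from the shortfall that the trial does not deliver its stated power, but the document does not support that: at the precision it uses, the power is delivered.
- **A ceiling, not an expectation.** The 10% is worded as an upper limit, and 364 is enough for every loss rate up to 9.34%. This narrows the failure to the last 0.66 points of the range. It does not remove it, because an allowance of up to 10% has to hold at 10%.
- **Which losses count.** The allowance pools withdrawal with loss to follow-up. Under Primary end-point, the outcome is read from the biopsy histopathology report, usually expected within 14 days of the procedure. A man who has a histology result and is lost before the 30-day assessments still contributes. Only men without a histology result reduce the sample behind the 80%, so the loss relevant to the primary comparison may well be below 10%. This also stands.
- **An unverified base.** The 79.7% takes 330 as giving exactly 80%. If 165 per arm was itself rounded up, power at 330 is slightly above 80% and the deficit smaller still. Without detection rates the 330 cannot be checked, so the figure is conditional. Whether 330 is right is a separate question that this point does not address.

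The size of the problem is therefore rightly played down. The arithmetic is untouched: 364 reproduces the multiplication by 1.1 exactly, so this is the wrong inflation step rather than a rounding choice.

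**Conclusion.** The point holds as a minor arithmetic inconsistency. The target was inflated by 1.1 instead of being divided by 0.9, so it covers a loss of 9.3% rather than 10%. At the full 10% about 327 to 328 men remain, some 2 to 3 short of 330.

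The finding of a shortfall needs only the three numbers in the paragraph and the reading of 10% as a share of those recruited. The power figure of about 79.7% also assumes that 330 gives exactly 80% and that every lost man lacks a histology result. The second assumption is the least favourable case. The result does not show an underpowered trial and does not by itself call for more recruitment.

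**What to change.** Keep 364 and correct the sentence in the sample-size paragraph in one of two ways:

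- state that 364 recruits (182 per arm) cover loss of up to about 9.3%; or
- keep the 10% and state that it would leave about 327 men, with about 79.7% power if 330 gives 80%.

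It would help to add that the loss in question is of men without a histology result. For reference, a target that covers a full 10% is 367, or 368 in equal arms (184 per arm).

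The cost is one sentence of Protocol wording and a slightly less generous stated allowance, with no change to recruitment or analysis.

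### Baseline adjustment is triggered by observed imbalance and fitted to clinically significant cancer, so the primary comparison of any cancer forgoes precision from age, PSA and DRE already recorded

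*Protocol*

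**What the plan says.** Under Study design and method, the Protocol gives an illustrative list of baseline items: age, height, weight, allergies, "past medical history, family history of PCa, drug history, presenting PSA and DRE findings". Three questionnaires (IPSS, EQ-5D-5L, IIEF) are also completed at baseline. Randomisation is 1:1 in permuted blocks of varying size, with no stratification factor stated.

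Under Statistical analysis, "Primary endpoint is difference in proportion of patients with PCa detected between the two cohorts based on histopathological analysis". The estimator is unadjusted: "Absolute differences in PCa detection rate will be calculated with 95% CIs". The decision is read from the lower confidence bound, against -5% for non-inferiority and against zero for superiority: "If lower bound is greater than 0, TP will be deemed superior".

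The same paragraph then calls for a comparison of the arms at baseline and continues: "If any imbalance were identified, a multivariable logistic regression analysis will be carried out". The dependent variable of that regression is clinically significant cancer. Its covariates are set by one sentence: "Any baseline characteristics imbalance will be used as a covariate". No test, threshold or list of candidate covariates is given. The next paragraph applies imbalance-triggered regression to the secondary outcomes, logistic for binary and linear for continuous ones.

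Under Primary end-point, cancer is defined as any cancer regardless of grade. Under Secondary end-points, clinically significant cancer is listed as a secondary outcome.

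**The concern.** In a properly randomised trial any baseline imbalance is due to chance. What adjustment gains depends on how well a covariate predicts the outcome, not on how unequal the arms happen to look. The rule reverses this. It would bring in height or allergies if they differed and leave out PSA if it looked balanced. PSA and DRE are the obvious candidates on the Protocol's own terms, because they are the grounds for referral and also define eligibility.

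Two things are at stake. First, the primary interval is wider than it needs to be, in a trial planned at only 80% power. Second, the adjusted analysis does not support the primary one. Its covariates are chosen from the data, its outcome is a secondary endpoint, and a logistic model yields an odds ratio, to which neither the zero bound nor the -5% bound applies.

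**Working it through.** **1. The plan's own figure.** The Protocol gives 330 men (165 per group), 80% power, a one-sided Z test at 0.05 and a superiority margin of 10%, but no detection rates. The 165 can therefore be neither confirmed nor refuted. With the pooled formula n = [z(0.95)·√(2p̄(1−p̄)) + z(0.80)·√(p₁(1−p₁)+p₂(1−p₂))]² / d²:
- 20% vs 32% gives 2.364/0.0144 = 164.2, so 165 per arm.
- 30% vs 43% gives 2.848/0.0169 = 168.5, so 169 per arm.

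The pair 30% vs 43% is used below as an assumption.

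**2. Gain from prespecified adjustment.** Let R² be the share of outcome variance explained by the covariates. The Protocol gives no value, so 5% to 20% is assumed. The standard error is multiplied by √(1−R²), and 330 men carry the information of 330/(1−R²) unadjusted men. At 30% vs 43% with 165 per arm, the unadjusted SE is √[(0.21+0.2451)/165] = 0.0525, and power is Φ(0.13/SE − 1.645).

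| R² | SE reduction | Equivalent N | 95% half-width (points) | Power |
|---|---|---|---|---|
| 0 | – | 330 | 10.3 | 79.7% |
| 5% | 2.5% | 347 | 10.0 | 81.5% |
| 10% | 5.1% | 367 | 9.8 | 83.3% |
| 15% | 7.8% | 388 | 9.5 | 85.1% |
| 20% | 10.6% | 413 | 9.2 | 86.9% |

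The Statistical analysis section mentions both 95% and 97.5% intervals. The proportional gain is the same for either.

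**3. Check by simulation.** The setting was 1,500 trials per scenario, 165 per arm, 30% detection with TRUSB, a true difference of about 8 to 10 points, and one baseline score standing for PSA, DRE and age (all assumed). The SD of the risk difference, unadjusted vs standardised, was:
- AUC 0.635: 0.0522 vs 0.0511
- AUC 0.702: 0.0516 vs 0.0482
- AUC 0.758: 0.0515 vs 0.0470

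Multiplied by 1.96, the half-widths fall from 10.2 to 10.0, from 10.1 to 9.4 and from 10.1 to 9.2 points, a gain of about 0.2 to 0.9 points.

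**4. What the imbalance trigger recovers.** A second simulation (330 men, three prognostic covariates, 1,500 runs per setting) took imbalance to mean p<0.05, which is an assumption. Variance relative to the unadjusted difference was:

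| Prognostic strength | Prespecified | Imbalance-triggered |
|---|---|---|
| Weak | 0.97 | 0.99 |
| Moderate | 0.86 | 0.97 |
| Strong | 0.72 | 0.93 |

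Mean estimates were essentially unchanged by prespecified adjustment (0.136 vs 0.136, 0.121 vs 0.121, 0.105 vs 0.106). This run applied the trigger to the primary outcome. As written, the Protocol fits the triggered model to a different outcome, so the primary difference recovers nothing.

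**5. How often the trigger fires by chance.** With k independent characteristics each tested at 0.05, the probability of at least one imbalance is 1 − 0.95^k. For the nine named items this is 37%, and with the three questionnaires (k = 12) it is 46%. Independence is an approximation. With no threshold stated, whether the trigger fires is a matter of judgement.

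**6. Primary analysis and triggered model side by side.**

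| | Primary decision | Triggered model |
|---|---|---|
| Outcome | Any cancer | Clinically significant cancer |
| Scale | Absolute difference | Odds ratio |
| Covariates | None | Those found imbalanced |

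The two differ in every row.

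**The case against.** The strongest reply is that nothing is invalid. An unadjusted risk difference is unbiased under randomisation and matches the Z test used for sample size. That stands.

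A reader might go further and infer that choosing covariates after seeing the data could carry the primary bound across 0 or -5%. The text does not support this. Those bounds are read from the absolute difference in detection of any cancer, with no covariate in it, and the triggered regression concerns another outcome on another scale. The secondary-outcome paragraph is phrased as though the primary had already been adjusted, which hints that adjustment was intended there too. But no rule lets the adjusted result replace the unadjusted one.

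A reader might also infer that prostate volume has been wrongly left out, since the background says TRUSB has difficulty reaching some tumours, "in particular in patients with a large prostate volume". That does not hold as a finding either. The baseline list is only illustrative, so absence from the plan is not shown. Volume measured at biopsy would also be missing for randomised men who are never biopsied, although an intention-to-treat analysis is planned.

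It is also fair that the gain is modest and rests on an assumed prognostic strength. Eligibility restricts age to 40–80, PSA to 20 ng/mL or below and DRE stage to T2 or below, which may weaken these markers, so the low end of the range is as compatible with the Protocol as the high end.

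Finally, a covariate list and an imbalance threshold are details that a SAP commonly fixes. But the trigger, the selection rule and the dependent variable are stated in the Protocol itself, and a SAP that follows it would inherit them.

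**Conclusion.** The point holds as a worthwhile improvement, not as a flaw that invalidates the primary test. The Protocol commits to an adjustment rule that depends on chance imbalance, selects covariates from the data, and uses an outcome and scale that do not match the primary decision. The unadjusted primary result stays valid, and its cost is lost precision: a standard error 2.5% to 10.6% larger than prespecified adjustment would be expected to give, relative to the unadjusted value, if R² is between 5% and 20%. At assumed rates of 30% vs 43%, that corresponds to power of 81.5% to 86.9% instead of 79.7%. R² and the detection rates are assumptions. The outcome mismatch and the data-driven covariate rule rest on the text alone.

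**What to change.** In the Statistical analysis section:
- Delete the imbalance trigger and the rule that any imbalanced item becomes a covariate. Keep the baseline comparison as description only.
- Prespecify log presenting PSA, DRE (normal/abnormal) and age, used whatever the observed balance.
- Use any cancer as the dependent variable for the primary analysis. Analyse clinically significant cancer separately, as the secondary outcome it is.
- Report the primary result as a covariate-standardised risk difference with its confidence interval, so that it is on the scale of the decision rule. Keep the unadjusted difference as a sensitivity analysis, and state in advance that the standardised difference governs the decision.
- Apply the same fixed-covariate approach to the secondary binary and continuous outcomes.

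The cost is a change of wording, best made before outcome data are seen. No extra patients, visits or data items are needed. The downside is a slightly more complex primary estimate. As the Protocol commits all analysis to SPSS, the sponsor should confirm that the standardised difference and its interval can be produced there, or name other software.
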